#### 1.4 Study rationale

As modafinil and armodafinil are newer drugs, there remains a paucity of research specifically in cancer. However, data from other chronic illnesses that have symptoms of fatigue and cognitive impairment, as well as preliminary data with modafinil in patients with brain tumors (59), provides the impetus to study the newer psychostimulants in patients with high grade glioma. Although large RCT's with modafinil and methylphenidate have not shown a significant impact on fatigue (47, 58), these trials did not focus on, and often did not include, patients with brain tumors, specifically glioblastoma. These studies do provide data to hypothesize that patients with more severe fatigue (48, 58) may benefit from these agents. Although data to date do not support using methylphenidate during radiation treatment (49), newer psychostimulants with broader CNS effects still need to be evaluated for effects on fatigue during and after radiation therapy, specifically in brain tumor populations. There are two clinical trials currently actively recruiting patients that involve armodafinil. Both are using heterogeneous populations of people with brain tumors and both are using armodafinil during radiation therapy (77, 78).

We conducted an extensive literature search and could find no published data on the effects of 250mg of armodafinil in treating fatigue in brain tumor patients. Given the trend toward positivity of the studies ongoing with 150 mg dose (77,78) further investigation is needed to decipher if further benefit from a higher dose is plausible. The 250 mg dose of armodafinil has been proven safe and efficacious in a study that showed positive results in patients with narcolepsy (109). In addition, there are ongoing trials listed on clinicaltrials.gov using 250mg of armodafinil in patients with results pending. Our proposed three-arm study complements both of those trials and other ongoing studies (110) by evaluating armodafinil in a more homogeneous population, specifically high grade glioma, and evaluating armodafinil for its effects on severe fatigue once radiation therapy has been completed. Given that fatigue is prevalent at the completion of radiation therapy, this seems the best endpoint to evaluate. Cognitive difficulties are one of the elements of fatigue and hence, these two problems are sometimes difficult to tease apart. Fatigue measurement is more advanced than cognitive measurement, due to problems with practice effects for neuropsychiatric measures and the lack of understanding of how fatigue, sleep and mood impact cognition. Therefore, we believe that evaluating fatigue as the primary endpoint and cognition as a secondary endpoint is well justified.

### 2.0 GOALS

#### 2.1 Primary

To determine preliminary efficacy measured by patient reported fatigue using the Brief Fatigue Inventory (BFI) at 8 weeks of two doses (150mg and 250mg) of armodafinil in treating moderate fatigue compared to placebo in patients with high grade glioma.

#### 2.2 Secondary

- 2.2.1 To evaluate the tolerability at 8 weeks of 150mg and 250mg armodafinil in this patient population**
- 2.2.2 To assess the effect of armodafinil at 8 weeks on cognitive function in patients with high grade glioma.**
- 2.2.3 To assess the impact of armodafinil on global quality of life and other fatigue endpoints in this patient population with high grade glioma.**
- 2.2.4 Explore the correlation between the BFI, PROMIS, and PRO-CTCAE measures, as well as, the relationship of fatigue and cognitive difficulties.**

### 3.0 PATIENT ELIGIBILITY

#### 3.1 Inclusion Criteria

- 3.1.1 **Age  $\geq$  18 years.**
- 3.1.2 **Diagnosed with glioblastoma, gliosarcoma, small cell or large cell glioblastoma, glioblastoma with oligo features, glioblastoma with primitive neuroectodermal tumor-like components (GBM-PNET) features, anaplastic astrocytoma, anaplastic oligodendrolioma, or anaplastic oligoastrocytoma who are clinically stable and have completed radiation therapy (excluding stereotactic radiosurgery)  $>21$  days prior to registration.** NOTE: Clinical stability will be defined as a stable or improved KPS compared to the prior month.
- 3.1.3  **$\geq 6$  score on the worst fatigue question of the BFI (Brief Fatigue Inventory, see appendix III Question 3).** It is not required for the patient to complete the entire BFI to meet this criterion.
- 3.1.4 **Undergone surgery (gross total or subtotal resection) or biopsy and will have been treated with concurrent radiation therapy and chemotherapy as standard of care for Glioblastoma, gliosarcoma, small cell or large cell glioblastoma, glioblastoma with oligo features, glioblastoma with primitive neuroectodermal tumor-like components (GBM-PNET) features, anaplastic astrocytoma, anaplastic oligodendrolioma, or anaplastic oligoastrocytoma patients.** Note: radiation must be completed per Section 3.1.2, but chemotherapy is allowed.

Patients who are currently using Optune® device will be eligible to participate in this trial.

- 3.1.5 **Negative serum pregnancy test done  $\leq 7$  days prior to registration only for women determined to be of childbearing potential by their treating physician.**
- 3.1.6 **Ability to complete questionnaire(s) by themselves or with assistance.**
- 3.1.7 **ECOG Performance Status (PS) of 0, 1, 2 or 3 (Appendix XV).**
- 3.1.8 **Provide informed written consent.**
- 3.1.9 **Willing to return to enrolling institution for follow-up (during the Active Monitoring Phase of the study).**
- 3.1.10 **Stable dose of corticosteroid  $\geq 14$  days prior to registration.**

#### 3.2 Exclusion Criteria

- 3.2.1 **Any of the following because this study involves an investigational agent whose genotoxic, mutagenic and teratogenic effects on the developing fetus and newborn are unknown:**
  - Pregnant women
  - Nursing women
  - Men or women of childbearing potential who are unwilling to employ adequate contraception
- 3.2.2 **History of hypersensitivity to other psychostimulants.**
- 3.2.3 **History of steroid psychosis.**
- 3.2.4 **Currently taking medications for attention deficit hyperactivity disorder, history of or currently taking medications for severe anxiety disorder, schizophrenia, or**

**substance abuse by patient record and/or self-report. Note: Patients who had childhood ADHD and no longer require treatment will be eligible to participate.**

**3.2.5 Currently using any other pharmacologic agents or nonpharmacologic interventions to specifically treat fatigue, including psychostimulants, antidepressants, acupuncture, etc. will be excluded.** Note: Antidepressants used to treat items other than fatigue (such as hot flashes or depression) are allowed if the patient has been on a stable dose for  $\geq$  30 days prior to registration and plans to continue for the duration of the trial.

Erythropoietin agents to treat anemia are allowed. Exercise is allowed.

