While no studies to date have examined the benefits of armodafinil in reducing CRF, pharmacokinetic evidence suggests it will be at least the equivalent of modafinil in doing so. The precise mechanism(s) through which armodafinil (R-enantiomer) or modafinil (mixture of R- and S-enantiomers) promote wakefulness is unknown. Both armodafinil and modafinil have shown virtually identical pharmacological properties in nonclinical animal and *in vitro* studies (64). Data held at Cephalon Inc. and reported on by Darwish and colleagues (65) shows that the S- and R-isomers of modafinil exhibited similar inhibition of binding and functional activity at dopamine, norepinephrine and serotonin transporters. They also reported that while the two isomers of modafinil have approximately equipotent pharmacological activity, the S-isomer is eliminated rapidly, having a half-life of 4-5 hours, whereas the R-isomer has a half-life of approximately 15 hours. Essentially, modafinil is the S-isomer and armodafinil is the R-isomer.

A pharmacokinetic comparison of modafinil and armodafinil found that at steady state, armodafinil produces consistently higher plasma drug concentrations late in the day than modafinil when compared on a milligram to milligram basis (65). The different pharmacokinetic profile of armodafinil may result in improved usefulness throughout the day in patients compared with modafinil (66). In other words, due to the longer acting R-isomer, armodafinil may result in better control of fatigue for a longer time throughout the day.

Armodafinil is a novel psychostimulant that has shown promise as a cognitive enhancer in normal adults and patient populations, including schizophrenia and attention deficit hyperactivity disorder (67-70). Commonly prescribed to treat MS-related fatigue (67), armodafinil is also an alertness-promoting agent that reduces lapses of attention and vigilance that are caused by sleep deprivation and fatiguing disorders (71-73). Indeed, it has been suggested that the nootropic effects of armodafinil may be magnified among people with pronounced fatigue and pre-existing cognitive difficulties (74, 75). As cancer patients frequently suffer from significant fatigue and neuropsychological deficits, armodafinil has strong potential as a highly efficacious cognitive enhancer in this population. Despite this, no published studies have examined the use of armodafinil to treat fatigue or cognitive impairment in cancer patients.

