**3.2.8 Any history of Tourette's syndrome or tic disorder.**

**3.2.9 Any history of or active glaucoma.**

**3.2.10 Any history of intractable epilepsy.**

**3.2.11 Any of the following co-morbid systemic illnesses** or other severe concurrent disease which, in the judgment of the investigator, would make the patient inappropriate for entry into this study or interfere significantly with the proper assessment of safety and toxicity of the prescribed regimens:

- History of myocardial infarction
- Unstable angina
- Left ventricular hypertrophy
- Mitral valve prolapse syndrome

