#### 15.1.2 Formulation

Commercial armodafinil (Nuvigil®) tablets contain 50, 150 or 250 mg of armodafinil and the following inactive ingredients: croscarmellose sodium, lactose monohydrate, magnesium stearate, microcrystalline cellulose, povidone, and pregelatinized starch.

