**15.1.7 Known potential toxicities**

The use of armodafinil is contraindicated in patients with hypersensitivity to armodafinil, modafinil, or any component of the formulation.

Use is not recommended in patients with a history of angina, cardiac ischemia, recent history of MI, left ventricular hypertrophy, or patients with mitral valve prolapse, who have developed mitral valve prolapse syndrome with previous CNS stimulant use.

Angioedema and hypersensitivity (with rash, dysphagia, and bronchospasm) have been observed with armodafinil. Small average increases in mean systolic and diastolic blood pressure were seen in patients with narcolepsy taking armodafinil when compared to placebo.

Serious and life-threatening rashes including Stevens-Johnson syndrome, toxic epidermal necrolysis, and drug rash with eosinophilia and systemic symptoms have been reported with modafinil, the racemate of armodafinil. Most cases have been reported within the first 5 weeks of therapy.

In pre-approval narcolepsy, OSA and SWD controlled trials of armodafinil, anxiety, agitation, nervousness, irritability, and depression were reasons for treatment

discontinuation more often than for placebo. Cases of suicide ideation were also observed in clinical trials.

The use of armodafinil may impair the ability to engage in potentially hazardous activities.

The agent should be administered at a reduced dose for patients with severe hepatic impairment. There is inadequate information to determine the safety and efficacy of dosing patients with severe renal impairment. Elimination of the agent and its metabolites may be reduced in elderly patients. Consideration should be given to the use of lower doses in this population.

Headaches are dose related and reported in > 10% of patients. Adverse reactions reported in 4 to 10% of patients include nausea (dose related), dizziness, insomnia (dose related), anxiety, and diarrhea. Adverse events reported in < 4% of patients include: depression (dose related), dyspepsia, fatigue, palpitations, rash (dose related), upper abdominal pain, agitation, anorexia, constipation, contact dermatitis, decreased appetite, depressed mood, attention disturbance, dyspnea hyperhidrosis, increased heart rate, flu-like syndrome, loose stools, migraine, nervousness, pain, paresthesia, polyuria, pyrexia, thirst, tremor, xerostomia (dose related), and vomiting.

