### **15.2 Placebo**

Placebo tablets will be purchased from PharmOps, Inc., Phillipsburg, NJ. The tablets will similar in appearance to the armodafinil tablets. The tablets will contain anhydrous lactose (bulking agent), microcrystalline cellulose (bulking agent/binder), crospovidone (disintegrant), and magnesium stearate (lubricant).

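### The exclusion criteria omit hypersensitivity to armodafinil or a tablet component, and most angina and ischemia, although Section 15.1.7 contraindicates or advises against the drug in these patients

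*Combined protocol and SAP*

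**What the plan says.** **Hypersensitivity.** The only allergy criterion is Section 3.2.2: "History of hypersensitivity to other psychostimulants". Section 15.1.7 goes further: "The use of armodafinil is contraindicated in patients with hypersensitivity to armodafinil, modafinil, or any component of the formulation". Section 1.3 places the study drug in the same class that 3.2.2 refers to: "Armodafinil is a novel psychostimulant that has shown promise as a cognitive enhancer".

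**Tablet contents.** Section 15.1.2 lists the inactive ingredients of the active tablets as "croscarmellose sodium, lactose monohydrate, magnesium stearate, microcrystalline cellulose, povidone, and pregelatinized starch". Section 15.2 lists those of the placebo as "anhydrous lactose (bulking agent), microcrystalline cellulose (bulking agent/binder), crospovidone (disintegrant), and magnesium stearate (lubricant").

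**Cardiac history.** Section 15.1.7 states: "Use is not recommended in patients with a history of angina, cardiac ischemia, recent history of MI, left ventricular hypertrophy", and adds mitral valve prolapse where the syndrome appeared on an earlier CNS stimulant. Section 3.2.11 lists any history of infarction, "Unstable angina", left ventricular hypertrophy and mitral valve prolapse syndrome. It also has a judgment clause for "other severe concurrent disease which, in the judgment of the investigator, would make the patient inappropriate for entry into this study" or would interfere with assessing safety.

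**Hepatic impairment.** Section 15.1.7 calls for a lower dose when hepatic impairment is severe. Section 7.1 fixes the daily dose at 150 mg or 250 mg, Section 8.0 provides only for stopping, and Section 15.1.8 buys only those two strengths.

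**The concern.** Eligibility criteria should make a known contraindication operative without anyone having to consult another section. Here the two sections disagree, and Section 3 is the one sites act on. Section 6.4.3 has staff confirm that the eligibility criteria are met, using the randomization forms as a tool. Section 13 defines an ineligible patient solely by those criteria. A patient with a past armodafinil reaction, or with stable angina, would therefore count as properly enrolled.

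What is at stake is patient safety. Section 15.1.7 itself reports angioedema and hypersensitivity with rash, dysphagia and bronchospasm on armodafinil. The test schedule in Section 4.0 lists no ECG and no liver test, so scheduled screening would not bring the cardiac or hepatic conditions to light.

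**Working it through.** The plan gives no figure to reproduce. The check is an item-by-item comparison of Section 15.1.7 with Section 3.2, followed by simple allocation arithmetic.

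| Item in 15.1.7 | Strength of statement | Matching criterion in 3.2 |
|---|---|---|
| Hypersensitivity to armodafinil | Contraindicated | None; *other* in 3.2.2 excludes it |
| Hypersensitivity to modafinil | Contraindicated | Arguably covered by 3.2.2 (Section 1.3 calls modafinil a CNS stimulant) |
| Hypersensitivity to a tablet component | Contraindicated | None |
| Any history of angina | Not recommended | Unstable angina only (3.2.11) |
| Cardiac ischemia | Not recommended | Infarction and unstable angina only (3.2.11) |
| Recent infarction | Not recommended | Covered, and stricter: any history |
| Left ventricular hypertrophy | Not recommended | Covered |
| Mitral valve prolapse syndrome | Not recommended | Covered, without the prior-stimulant condition |
| Severe hepatic impairment | Reduced dose | Not listed; at most the judgment clause in 3.2.11 |

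**Does the judgment clause close the gaps?** It is discretionary and limited to severe concurrent disease. A history of drug or excipient allergy is not a concurrent disease, and mild stable or past angina is not severe. Severe hepatic impairment fits the clause, but exclusion is permitted and not required.

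**Exposure given enrolment.** Allocation is balanced over three arms, two of them active (Sections 6.4 and 16.2, 100 evaluable patients per arm).

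- P(armodafinil) = 2/3 = 66.7%; P(250 mg) = 1/3 = 33.3%.
- For k such patients, P(at least one receives armodafinil) = 1 − (1/3)^k:
  - k = 1: 1 − 1/3 = 66.7%
  - k = 2: 1 − 1/9 = 88.9%
  - k = 3: 1 − 1/27 = 96.3%

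These figures treat allocations as independent. The dynamic allocation procedure makes them approximate. The value of k is assumed, because the documents give no frequency.

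**Excipients.** The active tablets have six inactive ingredients and the placebo has four. Three are in both: lactose (monohydrate in one, anhydrous in the other), magnesium stearate and microcrystalline cellulose. A patient allergic to one of these three is exposed in 3 of 3 arms, so a corrected criterion has to cover the placebo tablets too.

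**The case against.** The strongest reply accepts the text comparison and disputes its weight.

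- **The contraindicated group is small.** With modafinil arguably covered, what remains is a patient who has already reacted to armodafinil itself or who is allergic to a tablet excipient. The word *other* looks like a drafting slip, and a physician who reads Section 15.1.7 would probably catch a known armodafinil allergy. This stands as a point about frequency. It does not supply the missing criterion.
- **The angina statement is a caution, not a contraindication.** The protocol sets its own cardiac list, stricter than 15.1.7 on infarction and mitral valve prolapse. Nor does every caution have to become an exclusion: 15.1.7 also suggests considering lower doses in elderly patients, yet the trial stratifies on age 60 or over and nobody proposes excluding them. This is fair, and it makes the angina limb the weaker of the two. But that age caution concerns dose, whereas the angina caution concerns use at all. Section 3.2.11 otherwise follows the same sentence of 15.1.7 closely, and no reason is given for the narrower angina item.
- **Safeguards exist.** Treatment is under physician supervision (6.4.5), patients are told to watch for rash and itching (15.1.9), and the drug stops for related grade 3 or worse toxicity (8.0). The last two act only after exposure.
- **The percentages restate the allocation ratio.** That is correct. They describe exposure given enrolment and say nothing about how many patients are affected or their risk of harm.

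**Conclusion.** The concern holds. Two groups have no matching criterion: patients hypersensitive to armodafinil or a tablet component (contraindicated), and patients with stable or past angina or with ischemia short of infarction (not recommended). A third, severe hepatic impairment, is left to investigator discretion in a trial that offers no reduced dose.

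The hypersensitivity gap carries most of the weight and would justify the change alone. The number of patients affected is unknown; given enrolment, about two in three would receive armodafinil. The conclusion rests on reading *other psychostimulants* as excluding the study drug, which Section 1.3 supports, and on no other criterion in 3.1 or 3.2 covering these patients. Sample size, power, type I error and the endpoint are untouched. This is a cheap safety improvement to the eligibility wording.

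**What to change.** 1. Reword 3.2.2 as: *History of hypersensitivity to armodafinil, modafinil, any component of the study tablets (active or placebo), or other psychostimulants.*
2. In 3.2.11, replace the unstable angina item with: *History of angina or cardiac ischemia.*
3. Add to the 3.2.11 list: *Known severe hepatic impairment*, judged from history and existing records.
4. Keep the fixed doses, so that the blinded dose comparison is unchanged.

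Severe renal impairment, where 15.1.7 says only that information is inadequate, can be left to the sponsor's medical lead.

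The cost is a few words in Section 3.2 and an updated eligibility checklist, with no new test. A small, unquantified number of patients become ineligible, mainly those with past or stable angina, including some whose disease is remote or well controlled.

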**3.2.6 Anticipating surgery**

**3.2.7 Uncontrolled hypothyroidism, profound anemia** (hemoglobin level of  $<10$  g/dL  $\leq$  28 days prior to registration), or **untreated clinical depression** per physician discretion. Patients with stable, controlled depression or receiving treatment for hypothyroidism will be eligible, if they have been on a stable dose for the past 30 days and plan to continue for the duration of the trial.

**3.2.8 Any history of Tourette's syndrome or tic disorder.**

**3.2.9 Any history of or active glaucoma.**

**3.2.10 Any history of intractable epilepsy.**

**3.2.11 Any of the following co-morbid systemic illnesses** or other severe concurrent disease which, in the judgment of the investigator, would make the patient inappropriate for entry into this study or interfere significantly with the proper assessment of safety and toxicity of the prescribed regimens:

- History of myocardial infarction
- Unstable angina
- Left ventricular hypertrophy
- Mitral valve prolapse syndrome

**3.2.12 Receiving any medications or substances that are strong or moderate inhibitors of CYP3A4.**

Use of the following strong or moderate inhibitors are prohibited  $\leq$  7 days prior to registration:

Strong Inhibitors of CYP3A4:

> 5-fold increase in the plasma AUC values or more than 80% decrease in clearance  
Indinavir (Crixivan®)  
Nelfinavir (Viracept®)  
Atazanavir (Reyataz®)  
Ritonavir (Norvir®)  
Clarithromycin (Biaxin®, Biaxin XL®)  
Itraconazole (Sporanox®)  
Ketoconazole (Nizoral®)  
Nefazodone (Serzone®)  
Saquinavir (Fortovase®, Invirase®)  
Telithromycin (Ketek®)

Moderate Inhibitors of CYP3A4:

> 2-fold increase in the plasma AUC values or 50-80% decrease in clearance  
Aprepitant (Emend®)  
Erythromycin (Erythrocin®, E.E.S. ®, Ery-Tab®, Eryc®, EryPed®, PCE®)  
Fluconazole (Diflucan®)  
Grapefruit juice  
Verapamil (Calan®, Calan SR®, Covera-HS®, Isoptin SR®, Verelan®, Verelan PM®)  
Diltiazem (Cardizem®, Cardizem CD®, Cardizem LA®, Cardizem SR®, Cartia XT™, Dilacor XR®, Diltia XT®, Taztia XT™, Tiazac®)

**3.2.13 Receiving any medications or substances that are inducers of CYP3A4.**

Use of the following inducers are prohibited  $\leq$  7 days prior to registration

**Inducers of CYP3A4:**

Efavirenz (Sustiva®)  
Nevirapine (Viramune®)  
Carbamazepine (Carbatrol®, Epitol®, Equetro™, Tegretol®, Tegretol-XR®)  
Modafinil (Provigil®)  
Phenobarbital (Luminal®)  
Phenytoin (Dilantin®, Phenytek®)  
Pioglitazone (Actos®)  
Rifabutin (Mycobutin®)  
Rifampin (Rifadin®)  
St. John's wort

